1.5. Randomization and Blinding

Stratification

Dynamic randomization (ie, covariate-adjusted randomization) will be used to maintain balance between treatment groups with respect to the following stratification factors: AHA background (ie, diet and exercise only, metformin monotherapy, insulin monotherapy, or combination of metformin and insulin) and age group [≥ 10 to <15 years old, ≥ 15 to <18 years old]. The stratification process will be handled after logging on to the IWRS being used for the study.

Randomization

In dynamic randomization, a new subject is sequentially assigned to a particular treatment group by taking into account the specific covariates and previous assignments of subjects. This approach uses the method of minimization by assessing the imbalance of sample size among the covariates listed above. On Day 1, subjects will be randomized to 1 of 2 treatment groups based on a computer-generated dynamic randomization algorithm prepared by or under the supervision of the sponsor before the study. This approach seeks to maintain balance between treatment groups with respect to the AHA background and age group. The goal is to have at least 30% of randomized subjects that will be ≥ 10 to <15 years of age, 30% to 75% of participants will be female, and at least 20% in both age subsets (10 to <15 years, and ≥ 15 to <18 years) will be male, and 30% of participants that will have ethnicity and life-style comparable to Europe.

Re-randomization

At Week 12, subjects' glycemic status will be assessed by a central laboratory HbA_{1c} . Following the review of the Week 12 unmasked HbA_{1c} results and the Week 12 eGFR value, the following will occur:

- Subjects with HbA_{1c} value <7.0% or eGFR <60 mL/min/1.73 m2 will not be undergoing re-randomization and instead will be continuing their current treatment assignment (ie, canagliflozin 100 mg or matching placebo) for the remainder of the study.
- Subjects with HbA_{1c} value \geq 7.0% and eGFR \geq 60 mL/min/1.73 m2 will be re-randomized in a 1:1 ratio (in a blinded fashion via IWRS) to either.
 - remain on their original treatment assignment (ie, canagliflozin 100 mg or matching placebo) or
 - up-titrate canagliflozin 100 mg to 300 mg (or matching placebo). In order to keep the study blind, subjects randomized to the placebo group will undergo a mock up-titration.

Blinding

The investigator will not be provided with randomization codes. The codes will be maintained within the IWRS, which has the functionality to allow the investigator to break the blind for an individual subject.

2. GENERAL ANALYSIS DEFINITIONS

2.1. Visit Windows

The double-blind treatment phase will begin with the day when the first dose of double-blind study medication (either canagliflozin or placebo) is taken, which will be denoted as study Day 1. All efficacy and safety measurements at each visit will be assigned a study day relative to this date. All data collected on or after study Day 1 up to and including the End-of-treatment/Early Withdrawal (EOT/EW) visit will be considered within the double-blind treatment phase (ie, baseline through endpoint).

While the Time and Events Schedule of the protocol indicates the visit timing and procedures for each visit, the timing of a subject's actual visit may not be exactly as per the protocol indicated target day / visit window (note that the protocol does not indicate required visit windows, but rather provides clear guidance for visit timing). Consequently, for the purpose of analysis, the conventions outlined below will be used to allocate the data collected at each actual visit to a planned protocol visit by defining visit windows.

The reference day is study Day 1.

Baseline will be defined as the pre-dosing measure closest to or including Day 1 (prior to dose administration). If the pre-dosing measure on Day 1 is missing, the latest available measurement prior to Day 1 will be used.

If a subject has two or more actual visits in one analysis visit window, the visit closest to the target day will be used as the study visit for that analysis visit window. However, results from all visits will be included in the safety analyses (eg, pre-defined limits of change analysis) to assure that all on-treatment results are included. If two study visits are the same number of days from the target day within the same visit window, the later visit will be considered the study visit for that target

day. Even though all visits will be allocated an analysis visit window, only planned protocol visits for each variable will be included in the by-visit analyses.

Table 1 summarizes the analysis visit windows for laboratory, vital signs, physical examination, and other key safety variables.

Scheduled Visit Time (label on output)	Time Interval (Day) ^a	Target Time Point (Day)
Baseline	≤1 ^b	1
Week 6	1° to 64	43
Week 12	65 to 113	85
Week 20	114 to 162	141
Week 26	163 to 211	183
Week 34	212 to 267	239
Week 42	268 to 330	295
Week 52	≥ 331	365

 Table 1:
 Time Intervals for Analysis Visit Windows – Double-Blind Treatment Period

^a Relative to the day of the first dose of double-blind study medication.

^b Up to the first dose of double-blind study medication.

^c Immediately following the first dose of double-blind medication. For variables without time or reference collected at baseline, the first window after baseline starts on Day 2 according to the protocol.

2.2. Analysis Sets

Unless otherwise specified, all analyses will use the Full Analysis set (FAS), which is defined below. If additional subjects need to be excluded from the analysis sets, the subjects will be identified before database lock, and the reasons for the exclusion will be documented in the clinical study report.

2.2.1. Efficacy Analysis Set(s)

The FAS includes all subjects who are randomly assigned to a treatment group, have received at least one dose of study drug and have a baseline HbA_{1c} measurement.

The 26-week per protocol (PP) analysis set consists of all FAS subjects who complete the 26-week double-blind treatment period and have no major protocol deviations that may affect the interpretation of the primary efficacy endpoint (including but not limited to initiation of glycemic rescue therapy) within the 26 weeks of core double-blind treatment period.

The subjects who complete the 26-week core double-blind treatment period are defined as those subjects who receive study drug and have non-missing HbA_{1c} measurement at Week 26. In the case that the subjects discontinue from the treatment or have drug interruption at Week 26, the HbA_{1c} measurement needs to be taken no later than the last dose of study drug at Week 26 plus 7 days and the subjects' last dose date needs to be on or after Day 163 based on the visit windows in Table 1.

The 52-week PP analysis set consists of all FAS subjects who complete the 52-week double-blind treatment period (ie, documented in the eCRF by the investigator that the subject complete treatment in the study through the Week 52 visit) and have no major protocol deviations that may

affect the interpretation of the efficacy endpoint (including but not limited to initiation of glycemic rescue therapy) within the 52 weeks of treatment.

Major protocol deviations are defined in Section 4.5.

2.2.2. Safety Analysis Set

The safety analysis set consists of the subjects who are randomized and take at least 1 dose of study drug.

2.3. Definition of Subgroups

Subgroups are defined as follows:

- AHA subgroups: diet and exercise only; metformin monotherapy; insulin monotherapy; combination of metformin and insulin.
- Age: ≥ 10 to <15 years of age; ≥ 15 to <18 years.
- Sex: female; male.

3. INTERIM ANALYSIS AND DATA MONITORING COMMITTEE REVIEW

An Independent Data Monitoring Committee (IDMC) will be established to monitor safety data on an ongoing basis. A separate IDMC Charter will include an overview of the proposed summary tables/figures/listings to be provided to the IDMC by the Statistical Support Group. No interim analysis will be performed.

4. SUBJECT INFORMATION

4.1. Demographics and Baseline Characteristics

Baseline anthropometric and demographic characteristics will be summarized by treatment group and overall (all treatments pooled together) for the FAS and PP analysis sets. Descriptive statistics (N, mean, SD, median, and range) will be provided by treatment group for continuous variables such as age, body weight, and BMI at baseline.

The number and percentage of subjects in the categories of the following variables at baseline will also be summarized by treatment group:

- Age group: 10 to <15, ≥ 15 to <18 years old
- Sex: male, female.
- Race: White, Black or African American, Asian, American Indian or Alaska Native, Native Hawaiian or other Pacific Islander, Multiple, Not reported.
- Ethnicity: Hispanic or Latino, Not Hispanic or Latino, Not reported.
- AHA background: diet and exercise only, metformin monotherapy, insulin monotherapy, combination of metformin and insulin.

Descriptive statistics (N, mean, SD, median, and range) will also be provided by treatment group for baseline disease characteristics such as:

- HbA_{1c}
- FPG
- Body weight
- BMI
- Fasting plasma lipids (ie, LDL-C, HDL-C, total cholesterol, non-HDL-C, LDL-C to HDL-C ratio, non-HDL-C to LDL-C ratio, and triglycerides).
- SBP and DBP.
- Growth velocity and Tanner Staging.
- Markers of calcium and phosphate homeostasis (calcium, magnesium, phosphate, PTH, 25-hydroxy Vitamin D, calcitonin; urinary excretion of calcium and phosphate).
- Bone turnover markers (serum osteocalcin and serum collagen type 1 CTx).
- Urinary ACR.

The number and percentage of subjects with history of medical conditions by SOC and preferred term (based upon the general medical history [MH] eCRF) will be summarized by treatment group and overall.

4.2. Disposition Information

Subject disposition for all randomized subjects will be summarized by treatment group and overall using the following:

- Subjects who are randomized;
- Subjects who are randomized but not dosed (subjects excluded from the FAS);
- Subjects in the FAS;
- Subjects who complete the 26-week core double-blind treatment period (defined in Section 2.2.1);
- Subjects in the 26-week PP analysis set;
- Subjects who receive rescue therapy during the 26-week core double-blind treatment period;
- Subjects who complete the 52-week double-blind treatment phase (ie, investigator indicates on the eCRF [treatment disposition page] that the subject completed treatment);
- Subjects who receive rescue therapy during the 52-week double-blind treatment phase;
- Subjects in the 52-week PP analysis set;
- Subjects in the FAS who discontinue from treatment before the Week 52 visit (ie, investigator indicates on the eCRF [treatment disposition page] that the subject discontinued from the treatment prior to the Week 52 visit);
- Subjects in the safety analysis set.

For subjects who discontinue after randomization, the corresponding reasons for discontinuation from the treatment and discontinuation from the study will be summarized. Listings will be

provided for subjects whose predominant treatment differs from their randomized treatment and for subjects who temporarily take the wrong study medication.

For time to early discontinuation, Kaplan-Meier (KM) curves will be plotted by treatment group for the 52-week double-blind treatment phase. Descriptive analyses for the time to early termination will be provided.

4.3. Treatment Compliance

Treatment compliance will be based on the information from drug compliance eCRF page. The number and percent of subjects who have at least 75% study drug compliance from Baseline will be presented for Week 26 and Week 52 separately.

4.4. Extent of Exposure

Treatment duration is defined as the amount of elapsed time between the first and the last day that study medication was taken (inclusive). It will be calculated (in days) in terms of the difference in relative study days between the last and first dose of study medication, plus one day. If the end date of the medication intake is not known (e.g., subject is lost to follow-up), it will be imputed as the earlier of the disposition date (i.e., date of last contact with subject) or 28 days from the date that the last medication kit was dispensed.

Descriptive statistics (N, mean, SD, median, and range) will be presented by treatment group for treatment duration. The number of subjects with duration in each of the following categories (<2 weeks, 2 to <6 weeks, 6 to <12 weeks, 12 to <18 weeks, 18 to <26 weeks, 26 to <34 weeks, 34 to <42 weeks, 42 to <52 weeks, and \geq 52 weeks) will also be presented by treatment group as well as overall.

For subjects who discontinue from treatment prematurely (i.e., before Week 52), exposure will be summarized through the last day of dosing of double-blind study medication for that subject.

4.5. Protocol Deviations

The following list of protocol deviations may affect the interpretation of the primary efficacy endpoint and therefore, subjects with any of these protocol deviations will be excluded from the PP analysis set. The complete list of subjects with these protocol deviations will be identified prior to database lock and a summary of reasons for exclusion will be provided in the CSR.

- Subject has taken a prohibited medication including other SGLT2 inhibitors, or other AHAs that are not approved for use in pediatric population (including commercially available canagliflozin) for > 7 consecutive days within the last 90 days prior to the study's primary endpoint at Week 26 (excluding from 26-week PP analysis set) or at Week 52 (excluding from 52-week PP analysis set).
- Subject has had a change in his/her dose of background therapy during the double-blind period for ≥2 consecutive weeks within the last 90 days prior to the study's primary endpoint at Week 26 (excluding from 26-week PP analysis set) or at Week 52 (excluding from 52-week PP analysis set).

- Subject has taken pharmacologic (non-replacement) dose of a corticosteroid agent (oral or parenteral) for ≥2 consecutive weeks during the last 90 days prior to the study's primary endpoint at Week 26 (excluding from 26-week PP analysis set) or at Week 52 (excluding from 52-week PP analysis set).
- Subject has received study drug other than the one to which he/she was randomized for ≥2 consecutive weeks during the last 90 days prior to the study's primary endpoint at Week 26 (excluding from 26-week PP analysis set) or at Week 52 (excluding from 52-week PP analysis set).
- Subject has taken less than 75% of their double-blind study medication of either canagliflozin or placebo during the core double-blind treatment period (excluding from 26-week PP analysis set) or during the 52-week double-blind treatment phase (excluding from 52-week PP analysis set).

4.6. Prior and Concomitant Medications

Prestudy (i.e., medications taken before initiation and stopped prior to initiation of double-blind study medication) and concomitant medications (i.e., medications taken after initiation of double-blind study medication that were either started prior or after initiation of double-blind study medication) including antihyperglycemic agents (AHAs) and all other medications are collected (prestudy AHAs taken in the 6 months prior to study enrollment and other medications taken 30 days prior to enrollment).

All prestudy and concomitant medications are coded using World Health Organization Drug Dictionary (WHODD) and Anatomical Therapeutic Chemical (ATC) codes (Attachment 1).

Prestudy and concomitant medications will be summarized by the number of subjects taking pre-specified categories of medications by treatment group and overall.

5. EFFICACY

The efficacy analysis of the primary and secondary efficacy endpoints will be performed based on the FAS (Section 2.2.1). Assessment of the primary efficacy endpoint (i.e., change from baseline in HbA_{1c}) on the 26-week PP analysis set will be conducted as supportive analyses.

Regardless of the actual treatments the subjects receive, efficacy data will be analyzed according to the randomization assignment.

5.1. Analysis Specifications

5.1.1. Level of Significance

Unless otherwise specified, all statistical tests will be interpreted at a 2-sided significance level of 5% and all confidence intervals at a 2-sided confidence level of 95%.

To strongly control the family-wise error rate at the 5% significance level, a sequential testing procedure as illustrated in Figure 1 below will be applied. The primary endpoint will be first tested in all subjects (i.e., FAS), and if the results are significant (2-sided alpha level of 0.05), it will then proceed to test the subset of subjects on a background of metformin (with or without insulin).

Figure 1: Testing Sequence

As the secondary efficacy endpoints listed in Section 5.3 are supportive in nature, no corresponding hypothesis testing will be performed and therefore they are not included in the testing sequence above.

5.1.2. Data Handling Rules

For the endpoints at Week 12 and Week 26, data collected after Week 26 will be excluded from the statistical model. For the endpoints at Week 52, data collected up to Week 52 will be included in the statistical model.

For subjects who will be undergoing re-randomization, data collected during the Week 12 window will be considered in the statistical analysis only if the measurements are taken prior to the re-randomization date.

Unlike other assessments which were scheduled to be collected once at each visit, three consecutive readings of the SBP and DBP were taken (at intervals of at least 1 minute apart) and recorded. The average of the multiple measurements will be computed at each visit for all subjects and this averaged value will be used in all the analyses and summaries of blood pressure.

Unless otherwise stated, all efficacy analyses and summaries will be performed using the treatment groups assigned by Interactive Web Response System (IWRS).

5.2. Primary Efficacy Endpoint(s)

5.2.1. Definition

The primary efficacy endpoint will be the change in HbA_{1c} from baseline at Week 26.

5.2.2. Estimand

The clinical scientific question of interest is:

What is the mean treatment difference at Week 26 on change from baseline in HbA_{1c} expected from treatment assignment to either canagliflozin or placebo in children and adolescents with T2DM who have inadequate glycemic control, regardless of treatment discontinuation or initiation of rescue medication?

The primary efficacy estimand is described according to the following attributes:

- Population: children and adolescents (≥ 10 to <18 years) with T2DM who have an HbA_{1c} $\geq 6.5\%$ to $\leq 11.0\%$.
- Variable: change in HbA_{1c} from baseline to Week 26.
- Treatment: canagliflozin (100 mg or 300 mg) vs placebo.
- Intercurrent events (ICEs) (events that preclude observation of the variable or affect its interpretation): treatment discontinuation or initiation of rescue medication; ICEs are addressed with the treatment policy strategy, targeting the effect of treatment assignment, regardless of the occurrence of ICE.
- Population-level summary: difference in means versus placebo.

5.2.3. Analysis Methods

Primary Analysis

The primary analysis is based on the FAS dataset, including all HbA1c measurements collected from randomization to Week 26, including the measurements collected after treatment discontinuation or initiation of rescue medication.

The primary analysis will be based on pattern mixture model (PMM), as described below:

- Any intermediate missing data will be multiply imputed using Monte Carlo Markov Chains (MCMC), under a Missing at Random (MAR) assumption.
- Then the participants with ICEs and missing Week 26 HbA1c values will be multiply imputed using a multiple imputation (MI) model based on the participants with ICEs and non-missing Week 26 HbA1c values. An MI regression will be applied to impute all monotone missing values, using treatment group, stratification factors, baseline HbA1c and the change from baseline in HbA1c at Weeks 6, 12 and 20. If this MI model does not converge then a Copy Reference MI model will be used instead, as described in the sensitivity analysis section.
- Any Week 26 missing values for change from baseline in HbA_{1c} in participants without ICEs will be imputed based on the MI regression (see description above) applied to all participants.
- A total of 1000 multiple imputations will be performed. A seed equal to 345 will be used in all MI models.
- After MI, each of the multiply imputed datasets will be analyzed using analysis of covariance (ANCOVA) with terms for treatment, stratification factors, and baseline HbA_{1c}.
- Rubin's rules will be applied to combine the ANCOVA results across the imputed datasets, including the Week 26 LS Means for each treatment group and the difference vs placebo in LS Means.

Secondary analysis of the primary efficacy endpoint

The secondary analysis is based on a subset of subjects on background metformin (with or without insulin) from the FAS dataset, including all HbA1c measurements collected from randomization to Week 26, including the measurements collected after treatment discontinuation or initiation of

rescue medication. The attributes of estimand for this analysis is the same as the primary efficacy estimand except the population is a subset of subjects with background metformin (with or without insulin). The same analysis based on PMM will be performed as described above.

Bayesian analysis of the primary efficacy endpoint

Bayesian Analysis of the Primary Efficacy Endpoint for overall study and subset of subjects with metformin (with or without insulin) will be performed in the event that the study on its own yields non-significant result based on primary efficacy analysis. Full details of the Bayesian analysis will be included in a separate supplemental SAP.

Sensitivity and supportive Analyses

The following sensitivity analyses will also be performed, all aligned with the primary estimand:

- A Copy Reference MI model will be performed (Ratitch 2013). After any intermediate missing data will be imputed based on MCMC, monotone missing data will be imputed as following:
 - For the canagliflozin group, imputation will be performed using an imputation model based on the placebo/reference group, conditional on the stratification factors, baseline HbA_{1c} and the observed change from baseline values at previous time points relative to the mean of the model for the placebo group. Participants in the canagliflozin group will be imputed as if they had always been members of the placebo group.
 - For the placebo group, imputation will assume Missing at Random.
 - A total of 1000 multiple imputations will be performed. A seed equal to 345 will be used in all MI models.
 - After MI, each of the multiple imputed datasets will be analyzed using ANCOVA with terms for treatment, stratification factors, and baseline HbA_{1c}.
 - Rubin's rules will be applied to combine the ANCOVA results across the imputed datasets.
- A tipping point analysis will also be performed. This analysis starts with a MAR MI model (intermediate missing imputed with MCMC and monotone missing imputed with a MI regression model, using treatment group, stratification factors, baseline HbA_{1c} and the change from baseline in HbA_{1c} at Weeks 6, 12 and 20). Then each imputed value for monotone missing in the canagliflozin group will be made worse by a difference Delta. Each imputed dataset will be analyzed using ANCOVA and Rubin's rules will be applied to combine the ANCOVA results across the imputed datasets. A sequence of Delta worsening adjustments will be applied, starting with zero with increments of 0.1 until the results reach statistical non-significance. The results corresponding to all applied Delta adjustments will be plotted together with the results from the primary analysis, Copy Reference MI analysis and the other sensitivity analyses.
- The primary efficacy endpoint will be analyzed using a mixed model for repeated measures (MMRM) based on restricted maximum likelihood. The analysis will use the observed data and will include the fixed, categorical effects of treatment, stratification factors (ie, background AHA and age group), visit, and treatment-by-visit interaction, as well as the fixed,

continuous covariates of baseline and baseline-by-visit interaction. An unstructured covariance will be used to model the within-patient errors. In case the model does not converge using the unstructured covariance then alternative covariance structures (such as compound symmetry and AR(1)) will be considered.

• The change from baseline in HbA_{1c} will be analyzed using an ANCOVA model with treatment and the stratification factors as fixed effects and baseline HbA_{1c} value as a covariate. The treatment differences in the least-squares means and the 2-sided 95% CI will be estimated based on this model. The last observation carried forward (LOCF) method will be applied when the Week 26 values are missing.

In addition, based on the FAS with the data collected up to Week 26, the following supportive analysis will be performed:

- A re-randomization test (Proschan 2011) (utilizing the MMRM) will be used to determine the p-value for the treatment comparison of the primary efficacy endpoint (ie, comparing all subjects who are randomized to canagliflozin to all subjects who are randomized to placebo). The re-randomization test will fix the observed HbA_{1c} data, regenerate treatment assignments for the entire study using the same minimization algorithm employed in the study and compute the test statistics corresponding to the treatment comparison. This process will be repeated at least 1,000 times. The p-value for the treatment comparison will be defined as the proportion of re-randomized studies whose test statistic for that comparison is at least as extreme as that of the original treatment assignment.
- A supportive analysis of the primary endpoint will be conducted based on the 26-week PP analysis set using the same mixed model with repeated measures as in the sensitivity analysis.

Subgroup Analyses

Additional analyses of the primary efficacy endpoint in the FAS will be performed to examine if the treatment effect is different for the subgroups defined in Section 2.3. The interaction of treatment with each of the subgroups will be analyzed based on the MMRM model for the primary efficacy endpoint with the addition of the interaction term. If an interaction is observed (significance<0.10), then further evaluations will be performed to assess and explain the nature of the interaction [quantitative or qualitative interaction]. The LS mean change from baseline and the 95% CI for the LS means differences between canagliflozin compared to placebo will be presented for the subgroups.

In the event of small subgroups, descriptive statistics may be provided in lieu of model-based estimates.

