	have been updated based on adult data from Stenlöf (2013).		
Section 3. Interim Analysis and Data	Section streamlined with reference to the IDMC Charter for		
Monitoring Committee Review	further details.		
Section 5.1.1. Level of Significance	Text and figure describing the multiplicity adjustment have been		
	updated to accommodate the hypothesis testing for the subset of		
	subjects on a background of diet and exercise only.		
Section 5.2.3. Analysis Methods	Text to address the additional analyses of the change in HbA _{1c} in		
	AHA subsets has been added.		
References	The following reference has been added:		
	Stenlöf K, Cefalu WT, Kim KA, et al. Efficacy and safety of		
	canagliflozin monotherapy in subjects with type 2 diabetes		
	mellitus inadequately controlled with diet and exercise. Diabetes		
	Obes Metab. 2013;15(4):372-382.		

Amendment 2 (11 May 2023)

Applicable Section(s)	Description of Change	
The purpose of this amendment is to make this document consistent with Protocol Amendment 4 in terms of the		
analysis specifications and other pertinent details including the primary efficacy analysis based on the pattern		
mixture model. An additional analysis of primary efficacy endpoint using informative Bayesian Prior is add		
due to revised estimates of the treatment effect and the standard deviation specified in the Written Reque		
Amendment 5. This analysis will be performed	d in the event that the study on its own does not yield significant	
results based on primary efficacy analysis. Tw	o additional sensitivity analyses of the primary efficacy endpoint	
are also included. Clarifying text is added as a	pplicable and minor typographical errors are also addressed.	
Section 1.4. Sample Size Justification	This section is updated to make it consistent with Protocol	
	Amendment 4	
Section 5.1.1. Level of Significance	Text and figure describing the multiplicity adjustment have been	
	updated to reflect the deletion of the hypothesis testing for the	
	subset of subjects on a background of diet and exercise only and	
	make it consistent Protocol Amendment 4.	
Section 5.2.2 Estimand	Section updated to be consistent with Protocol Amendment 4	
Section 5.2.3. Analysis Methods	Details of the primary and secondary efficacy analyses of the	
	primary efficacy endpoint using pattern mixture model have been	
	added. Text added to mention that Bayesian analysis of primary	
	efficacy endpoint will be performed in the event the primary	

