1.3. Statistical Hypotheses for Trial Objectives

In children and adolescents (≥ 10 to <18 years) with T2DM who have inadequate glycemic control (ie, HbA_{1c} of $\geq 6.5\%$ to $\leq 10.5\%$), either on diet and exercise only, or on diet and exercise and metformin monotherapy, on diet and exercise and insulin monotherapy or on diet and exercise and combination of metformin and insulin:

Primary Hypothesis

• After 26 weeks of treatment, canagliflozin reduces HbA_{1c} relative to placebo.

Secondary Hypotheses

- After 26 weeks of treatment, canagliflozin reduces HbA_{1c} relative to placebo in the subset of subjects on background of metformin (with or without insulin).
- After 26 weeks of treatment, canagliflozin reduces HbA_{1c} relative to placebo in the subset of subjects on a background of diet and exercise only.

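### Does a Bayesian re-analysis triggered by a failed primary test, plus a leftover diet-and-exercise hypothesis, break the SAP's 5% family-wise error control?

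*SAP*

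**What the plan says.** SAP 5.1.1 introduces the multiplicity procedure with "To strongly control the family-wise error rate at the 5% significance level, a sequential testing procedure". The primary endpoint is tested first in the full analysis set (FAS). Only if that is significant at two-sided 0.05 does the plan move on to the metformin subset. Protocol 11.3.2 has the same two steps. The other secondary endpoints are excluded from formal testing.

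SAP 5.2.3 then has a separately headed Bayesian item on the same endpoint. It covers both populations in the sequence, and it "will be performed in the event that the study on its own yields non-significant result based on primary efficacy analysis". As to the specification, the SAP says only this: "Full details of the Bayesian analysis will be included in a separate supplemental SAP". The Amendment 2 entry in the SAP's amendment history calls the prior informative and gives the reason for the addition: Amendment 5 of the Written Request had revised the assumed effect and SD.

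SAP 1.1 and 1.3 still carry an objective and a secondary hypothesis of an HbA1c reduction "relative to placebo in the subset of subjects on a background of diet and exercise only". They also keep an upper HbA1c limit of 10.5%, where SAP 5.2.2 and the protocol have 11.0%. Protocol Amendment 4 removed the diet-and-exercise objective and hypothesis, and SAP Amendment 2 records deletion of the corresponding test from 5.1.1.

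**The concern.** An extra analysis that borrows outside information and runs only after the primary test has failed can work in one direction only: it can rescue a failed trial but never overturn a successful one. By the rule in 5.1.1 the metformin hypothesis is closed once the FAS test fails, yet the Bayesian item covers that subset too. Section 5.2.3 does not say the result is supportive, although the SAP labels other analyses that way. If the Bayesian result could carry an efficacy claim, the false-positive rate would be the chance that either route succeeds, and the 5% statement could be untrue.

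The diet-and-exercise hypothesis adds to this impression. It is listed as a formal hypothesis, has no position in the sequence and therefore no alpha. A reader of section 1.3 alone would expect it to be tested.

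**Working it through.** **The plan's own figure.** From SAP 1.4: effects 0.5, 0.4 and 0.5; half of subjects re-randomized, 1:1; SD 0.9; two-sided alpha 0.05; power about 85%.

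- Weighted effect = 0.5 × 0.5 + 0.25 × 0.4 + 0.25 × 0.5 = 0.475.
- The t-test needs 66 per group, giving 85.3% power. This matches the stated 66, and 66 × 1.1 = 72.6, rounded up to the stated 73 per arm.

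**The sequence as written.** The metformin test is reached only after a significant FAS test at 0.05, so under any combination of true nulls the chance of at least one false rejection is at most 0.05. The claim in 5.1.1 is correct for the procedure it describes.

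**What a Bayesian route could add, if it counted.** None of the prior mean, prior weight or success threshold is in these documents, so all three are assumptions here.

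- Data: estimate with SE s = 0.9 × √(2/66) = 0.157.
- Prior: mean μ, worth m subjects per arm, so its information relative to the trial is r = m/66.
- Success: posterior probability of benefit at least θ. This happens when the observed z exceeds k = z_θ × √(1 + r) − r × μ/s.
- One-sided error at zero effect: 1 − Φ(k). The frequentist test already succeeds at z > 1.96, so the combined error is the larger of this and 2.5%.

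Example with μ = 0.475, m = 5, θ = 97.5%: r = 0.0758, μ/s = 3.03, k = 1.96 × 1.037 − 0.230 = 1.803, error 3.6%. The same step with θ = 99%: k = 2.326 × 1.037 − 0.230 = 2.183, error 1.5%.

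| Assumed prior mean and threshold | m = 5 | m = 10 | m = 20 | m = 33 |
|---|---|---|---|---|
| 0.475, 97.5% | 3.6% | 5.0% | 9.4% | 18.8% |
| 0.2375 (half the effect), 97.5% | 2.8% | 3.0% | 3.8% | 5.0% |
| 0.475, 99% | 1.5% | 2.1% | 4.1% | 9.1% |

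The first two entries of the last row are below 2.5%: the Bayesian boundary is then stricter than 1.96, so a failed primary test could never be rescued in favour of canagliflozin.

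For the metformin subset, take 30 evaluable per arm (33 less 10%), planned effect 0.5 × 0.75 + 0.25 × 0.65 + 0.25 × 0.75 = 0.725, and s = 0.9 × √(2/30) = 0.232. At a 97.5% threshold the error is 5.5%, 11.1% and 32.6% for m = 5, 10 and 20.

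The answer therefore runs from no inflation to severe inflation, depending entirely on inputs assigned to another document.

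**The diet-and-exercise hypothesis.** Set side by side:

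- Protocol 2.1 and 2.2: metformin-subset objective and hypothesis only.
- SAP 1.1 and 1.3: diet-and-exercise objective and hypothesis still present.
- SAP 1.4: no sample size for that subset.
- SAP 5.1.1: no such step.
- SAP 2.3 and 5.2.3: these subjects appear only as one level of the background-therapy subgroup analysis.

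If someone did test the subset at 5% outside the sequence, a bivariate normal with correlation √(subset share) gives a family-wise rate of 9.5% at a 10% share and 8.9% at a 30% share. No section plans that test, so these figures describe nothing the trial will do.

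**The case for a change.** The best argument for a change is that the SAP labels its other non-confirmatory analyses with care. Secondary endpoints are called supportive, the dose comparisons are for reference, and the MMRM, LOCF, tipping-point and per-protocol analyses sit under a sensitivity and supportive heading. The Bayesian item sits above that heading, beside the primary and secondary analyses, without a label. A purely supportive analysis also has little reason to depend on failure of the primary test. Since the 5% claim is made in this document, its limits arguably belong here too.

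What stands is that the inferential role is not stated in the SAP's text. That is missing detail, and the SAP says where the detail will be. Silence here does not show that the supplemental SAP leaves the role, prior or threshold open.

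The available remedies do not improve on this:

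- Running the Bayesian analysis whatever the primary result changes no error rate. Given its role, it yields the same answer on the same data.
- Barring it from ever supporting a claim would settle, from outside, a question that the Written Request behind Amendment 2 may already address. That is a debatable policy choice and not a correction.

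**Conclusion.** The stated 5% control is true of the procedure it describes, and no text gives the Bayesian result a way to declare success. The analysis is announced in a dated amendment with a reason, and its specification is assigned to a named document. Family-wise control would be lost only if that result could support a claim and its prior and threshold together gave a boundary looser than 1.96. Under the assumptions shown, the one-sided error in all subjects ranges from 1.5% to 18.8%, so no single figure can be defended from these documents. A heavier or more favourable prior would do worse.

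The diet-and-exercise objective and hypothesis, and the 10.5% limit beside them, are clerical leftovers from before Protocol Amendment 4. The testing sequence, sample size section, estimand and protocol all agree against them, so an analyst following section 5 would run the right tests in the right population. No planned result depends on the stale wording, and no change to the plan follows.
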